1. Blinding Plan: This is a double-blind study whereby the investigators, research assistants, research nurse and participants will be blinded as to the drug treatment designation. Once participants have been assessed for eligibility and enrolled in the study, they will be randomized into 1 of 3 different groups. Participants randomized to either group I or II will be blinded to the intervention fantibiotic instillation in group I or placebo (saline alone) in group II]. Gentamicin sulfate will be prescribed for the research participants by the study physician or nurse practitioner and instilled under the direction of the research nurse. Thus, the participants in groups I and II will not be able to discern their assigned treatment. To ensure the double-blind, only the study physician or nurse practitioner as well as the pharmacy, all of whom are not associated with the data collection or data analysis, will be un-blinded. Note, the research nurse assisting participants with the instillation will be blinded. All participants will be identified by number and the instillation solutions (gentamicin or placebo) will be numbered with the pharmacy having access to the code specifying which instillations are active and which are placebo for each participant. The investigators and direct research team members will not be permitted to have knowledge of the group assignments. In the case of a drug related adverse event, the study physicians will evaluate the event and prescribe treatment that will minimize or completely resolve the event if minor or moderate in severity and it does not interfere with activities of daily living or quality of life (as determined by the participant). Should it be determined that the event has gotten worse, or if the participant can no longer tolerate the event, the study drug will be discontinued, and the participant will be terminated from study participation. There are no expected reasons to unmask the study treatment. The study physician or nurse practitioner will decide if the blind is to be broken or not. The blind will not "routinely" be broken when a serious adverse event (SAE) occurs. If an SAE is probably or definitely drug-related, the drug/placebo intervention will be stopped, and the participant treated appropriately. Emergency drug code envelopes will be created by the pharmacy at the study site. These will be labeled by participant randomization number and contain information, which will un-blind the treatment of the individual subject. These envelopes are to be used only in extreme emergencies, such as when an emergency situation exists in which the participant's treatment would be affected by knowledge of his drug therapy, and there is no time to contact the Medical Monitor. Note, that at the end of the study, participants will be un-blinded to the intervention designation by the study physician or nurse practitioner. If a participant was randomized to the no instillation group, however, he/she may re-enroll into the study and directly receive the gentamicin intervention and are not required to wait until the end of study, as all parties are un-blinded and aware of the treatment (standard of care) in this instance. All data from participants re-enrolling into the gentamicin-only group will be kept separate from those who are enrolled in the main study who are blinded.

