
The following participant withdrawal criteria may be implemented in determining when and how to withdraw participants from the trial/investigational product treatment.

Drug Discontinuation Criteria:

The subject's participation may be terminated for safety precautions based on any of the following by the study investigator. 1) Drug-related severe adverse event; 2) UTI requiring intravenous antibiotics; 3) Diagnosis of systemic absorption; 4) Diagnosis of nephrotoxicity; 5) Diagnosis of ototoxicity; 6) Diagnosis of renal failure

Temporary Discontinuation Criteria:

Situations of temporary discontinuation of study drug followed by subsequent resumption of study drug are: 1) Resolution of an adverse event, especially in cases where it is determined that the study drug was unlikely to have caused the event. 2) Resolution of a symptomatic UTI.

Withdrawal from Study:

A participant may withdraw from study participation at any time. Whatever data has been collected at the time of study termination will be evaluated by the PI for use in the final study database. If a participant is terminated from the study, the investigator will have the option to recruit an additional participant. Of withdraw from the study was due to an adverse event, participants will be followed until complete resolution of the adverse event that was possibly or definitely drug-related.

2. Statistical Plan: Data will first be summarized. We will use means with associated standard deviation, median with associated interquartile range and full range (min-max) to summarize continuous variables. Categorical variables will be summarized with frequency count and standard deviation. We will perform 2 types of analyses: pre-post differences within each group and between group comparisons of the differences. To evaluate the pre-post changes in each group, we will use paired t-test. To compare the changes between the 3 groups, we will use ANOVA test. If the ANOVA test yields significant results, we will perform follow-up 2 by 2 group comparisons using 2-sample t-tests. If the underlying assumptions of these tests are not satisfied, we will use the non-parametric equivalent tests instead.

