A medical event is defined within our program as any untoward or unfavorable medical occurrence in a human research participant that occurs during the enrollment period of a study. All medical events for study participants will be recorded in a log for tracking and reporting, as the team is made aware of them. Medical events that occur during a research visit will be reported to the study nurse and then elevated to the study physician if not immediately resolved. The physician will evaluate these medical events, to determine causality with relation to the research and referral for medical care. A weekly report of all medical events is generated by the research nurse and sent to the study physician (and physician assistant), the principal investigator, the regulatory core, and the study physical therapists for review of causality and follow-up. We have developed a table outlining the most common expected events in our SCI population. These events occur with this population on a daily basis. This table will allow the IRB and our staff to understand how expected and unrelated events will be documented and reported. If a physician outside the study team treats the medical event, the study physician will follow the event to assess the following:

- The medical condition affecting their medical eligibility for research
- Determination on causality of the event
- The event's effect on research assessments or training paradigms

All conclusions reached by the study physician will be reported to the PI. If another physician treats the medical issue the study physician will follow the individual to only assess whether the medical condition affects their medical eligibility in the study or any of the research assessments or training paradigms and will notify the principal investigator. These non-study related medical events are followed by the research team and will be reported to the IRB as outlined in Medical Reporting Table. A weekly report of all medical events is generated by the research nurse and sent to the study physician (and physician assistant), the principal investigator, and the study physical therapists. In this study, a medical event will only be reported if it occurs on the same day that the assessment associated with this study also occurs.

5. Data Safety and Monitoring Plan

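### Section III.E.4 both requires and excludes a causality determination when an outside physician treats a medical event, so a drug-related event could be handled as unrelated without being assessed

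*Combined protocol and SAP*

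**What the plan says.** All of the conflicting text is in Section III.E.4 of the combined protocol and SAP.

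- **First rule.** "If a physician outside the study team treats the medical event, the study physician will follow the event to assess the following": a list of three items then follows, namely eligibility, "Determination on causality of the event", and the effect on research assessments or training.
- **Second rule.** Shortly after that list comes a sentence for the case where "another physician treats the medical issue the study physician will follow the individual to only assess whether the medical condition affects their medical eligibility". Its remainder adds the effect on research assessments or training, with notice to the principal investigator. Causality is not among the items.
- **Label.** The next sentence reads "These non-study related medical events are followed by the research team and will be reported to the IRB as outlined in Medical Reporting Table".

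The section also describes the weekly medical event report twice. The first description sends it to a group that includes the regulatory core and gives causality review as a purpose. The second omits both. The closing sentence restricts reporting to events that fall on the day of a study assessment.

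Elsewhere, the Blinding Plan (II.B.1) states: "If an SAE is probably or definitely drug-related, the drug/placebo intervention will be stopped". Under Withdrawal from Study, when withdrawal was due to an adverse event, "participants will be followed until complete resolution of the adverse event that was possibly or definitely drug-related".

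**The concern.** The two rules have the same trigger, treatment by a physician outside the team, and differ on whether causality is assessed. Staff cannot follow both. Under the second, an event passes to the non-study-related route with no step at which its relation to the instillation is considered.

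This matters because other parts of the protocol act on relatedness. Outside treatment is also foreseeable: most instillations may be done at home once blood pressure is stable (II.B and the instillation procedures), and the protocol itself anticipates involvement of primary care and emergency services. If an outside-treated event is never assessed, the relatedness-based rules may not be triggered for that participant, and the count of related events in the gentamicin arm may be too low.

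**Working it through.** No arithmetic applies: the plan states no figure on this point, and the question is whether the sentences can stand together.

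**1. Is the trigger the same?** Yes. The first rule speaks of a physician outside the study team and the second of another physician. In context both mean someone other than the study physician who is treating the participant.

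**2. What differs?**

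| Item assessed by the study physician | First rule | Second rule |
|---|---|---|
| Eligibility for the research | Yes | Yes |
| Causality | Yes | No; the word *only* shuts it out |
| Effect on research assessments or training | Yes | Yes |

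The second rule is thus wider than eligibility alone. The single item it drops is causality.

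**3. Does any text limit the second rule to events already judged unrelated?** The section title refers to events unrelated to the study, but no sentence states that condition. The section defines a medical event as any unfavorable occurrence during enrollment and itself assigns causality determinations, so its content is not confined to events known to be unrelated.

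**4. Which rules need a causality determination?**

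- II.B.1: stopping the intervention when an SAE is probably or definitely drug-related.
- Drug Discontinuation Criteria, ground 1: a severe adverse event that is drug-related.
- Withdrawal from Study: follow-up to resolution when the event was possibly or definitely drug-related.
- III.E.3: return to supervised laboratory sessions when an SAE results from instillation or clamping.

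**5. Which safeguards work without the study physician's determination?**

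- Discontinuation grounds 2 to 6 (UTI needing intravenous antibiotics, systemic absorption, nephrotoxicity, ototoxicity, renal failure) are not worded in terms of relatedness.
- The first weekly-report sentence provides a causality review, but the second description omits it.
- Under III.E.5 the principal investigators review and report all adverse events, and the Medical Monitor sees SAEs in real time and other adverse events in annual aggregate. Neither is named as the person who determines causality for outside-treated events.
- Blood counts and metabolic panels at midpoint and after the intervention (Figure 2) are done whoever treats the participant.

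**6. Do the reporting sentences agree?** No. The same-day limit in III.E.4 does not fit with III.E.5, under which all adverse events are reported. An outside-treated event on a day without an assessment falls under both.

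**The case against.** The best defense is that the section runs in sequence: causality is reviewed first, the study physician's conclusions go to the principal investigator, and the later sentence then covers follow-up of events already found unrelated. The section title and the label fit that reading, and the Medical Reporting Table, which is not in the text reviewed, may settle the routing. The reading is coherent and may be what was meant. It is not what is written: the second rule is triggered by who treats the participant, and no prior judgement is mentioned.

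The defense is right on consequences. A reader might infer that relatedness is formally decided by who gives treatment, or that the stopping and follow-up rules cannot operate. The documents support neither. The first rule, the weekly causality review and the III.E.5 reviews remain in force, and kidney problems, hearing problems and infections needing intravenous antibiotics have their own discontinuation grounds.

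A reader might also try to calculate how far the count of related events would be biased. That would need the share of events treated outside and the share of those that every backstop misses. The documents give neither. The place of instillation does not supply them: III.E.3 tells participants to call the research team at once about bladder-distention complications at home, and the home program keeps one laboratory day a week.

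**Conclusion.** The contradiction is established from the wording alone and needs no assumption about event rates. The consequence is a possible failure to attribute drug-related events treated outside the team. It arises if staff follow the later sentence and the partial backstops do not catch the event. Its size is unquantified, and a claim that the safety results would be biased by a stated amount is not supported.

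The point goes beyond missing detail, because the protocol states a rule that excludes the assessment on which its other safety rules rely. It should be corrected.

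**What to change.** Amend Section III.E.4 as follows.

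1. Delete the sentence that limits the study physician when another physician treats the issue, and remove the unconditional non-study-related label from the sentence after it.
2. Apply the existing three-item list, including causality, to every medical event whoever treats it, and name who makes the determination.
3. Route an event as unrelated under the Medical Reporting Table only after causality has been determined and recorded.
4. Merge the two weekly-report descriptions, so that it is clear whether causality review and the regulatory core are included.
5. Reconcile the same-day reporting limit with the reporting of all adverse events in III.E.5. Otherwise an outside-treated event on another day could still go unreported after steps 1 to 3.

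The stopping and discontinuation criteria themselves need no change for this purpose.

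The cost is one wording amendment and some continuing work to obtain outside treatment records. The record requests in III.B are for eligibility, so this would be an added task. No additional participants or study procedures are needed.
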